4.5. Visit 4 (Day 21 ± 1)

Subjects will be asked to visit the site on Day 21 ± 1 (Visit 4). The predose FEV1 readings will be taken in the morning. Highest value from three acceptable readings will be considered. Measurement of vital signs, general and systemic examination, and AE monitoring will also be done. Compliance of subject diary, study medication and concomitant medication will be checked.

Table VI Procedures from Day 21 ± 1

Procedure	Treatment Period
	Day 21 ± 1
General & Systemic Examination	X
Vital signs	X
Spirometry	X
Study Drug Administration	One inhalation two times daily

	from Day 15 to Day 42
Subject Diary Card Compliance	X
Concomitant Medication check	X
Adverse event recording	X

- General and Systemic examination includes head, neck, eye, ENT, skin & appendages, renal, cardiovascular, pulmonary, reproductive, endocrine, gastrointestinal, nervous system, musculoskeletal, peripheral vascular and psychiatric
- Vital signs include Blood Pressure (Supine), Respiration Rate, Pulse Rate and Body Temperature in^oF/^oC.

4.6. End of Study (Day 42 ± 2)

Subjects will be asked to visit the site on Day 42 ± 2, End of Study/EOS (Visit 5). The FEV1 readings will be taken before morning dosing of inhaled medication corresponding to the time (with a window period of ± 30 min) of predose FEV1 taken on the 1st day of the start of the treatment. Two spirometry sessions with at least 3 acceptable readings each will be performed. Highest value from both the sessions will be noted. Average of both the highest readings will be considered as EOS FEV1 value. An exhaled nitric oxide (FeNO) test will be performed. The Asthma Control Test (ACT) questionnaire will be evaluated and the Investigator’s Global Evaluation will be performed. Measurement of vital signs, general and systemic examination, concomitant medication recording and AE monitoring will also be done. Subject diary, study medication and rescue medication will be collected from the subjects and efficacy evaluation will be done. Clinical laboratory tests will be repeated to check safety of subjects. Urine Pregnancy Test will be done for females of child bearing potential.

Table VII shows a list of all procedures to be completed on End of Study.

Table VII: End of Study

Procedure	End of Study
	Day 42 ± 2
General & Systemic Examination	X
Vital signs	X
Urine Pregnancy Test (for females of child bearing potential)	X
Laboratory Investigations	X
FeNO estimation	X
Spirometry	X
Subject Diary Card Compliance	X
Concomitant Medication check	X
Adverse event recording	X
Asthma Control Test Questionnaire	X

Procedure	End of Study
	Day 42 ± 2
Investigator's Global Evaluation	X
Collection of subject diary, study drug and rescue medication canister	X

- General and Systemic examination includes head, neck, eye, ENT, skin & appendages, renal, cardiovascular, pulmonary, reproductive, endocrine, gastrointestinal, nervous system, musculoskeletal, peripheral vascular and psychiatric
- Vital signs include Blood Pressure (Supine), Respiration Rate, Pulse Rate and Body Temperature in⁰F/⁰C.
- Haematology panel includes haemoglobin, haematocrit, white blood cell count with differential cell count, red blood cell count and platelets. Serum chemistry panel will include blood urea nitrogen, creatinine, albumin, alkaline phosphatase, total bilirubin, aspartate aminotransferase, alanine aminotransferase, random blood sugar, sodium, potassium, and chloride.

On Visit 5, subjects will be asked to complete all other end of study procedures. The subjects are required to submit their issued study drug and subject diaries for compliance checking.

4.7. Withdrawal Visit

A subject must be prematurely withdrawn from the study if the subject fulfills any of the withdrawal criteria specified in **Section 5.4**. In addition to the withdrawal procedures including General and Systemic Examination, Vital Signs, Urine Pregnancy Test and Clinical Laboratory Tests, the details of concomitant therapies will also be recorded.

5.0 STUDY POPULATION

5.1. Number of subjects

Assuming 5% loss from Enrolled population to mITT population, 1550 subjects will be enrolled in this study. Subjects will be enrolled in 2:2:1 proportion (Test: RLD: Placebo respectively) as 620:620:310.

5.2. Inclusion criteria

1. Adult male or female subjects of aged ≥ 18 to ≤ 65 years inclusive.
2. Diagnosis of asthma as defined by the National Asthma Education and Prevention Program at least 12 months prior to screening.
3. Pre-bronchodilator FEV1 of $\geq 45\%$ and $\leq 85\%$ of predicted value during the screening visit and on the first day of treatment visit.
4. $\geq 15\%$ and > 0.20 L reversibility of FEV1 within 30 minutes following 360 mcg of Salbutamol inhalation (pMDI) on the first day of treatment visit.
5. Subjects with FeNO > 25 ppb at screening and on the first day of treatment visit.
6. Subjects stable on their chronic asthma treatment regimen for at least four weeks prior to enrollment.
7. Subject should be able to replace current SABAs with Salbutamol inhaler for use as needed for the duration of the study.
8. Subject should be able to withhold all inhaled SABAs for at least six hours prior to lung function assessments on study visits.
9. Ability to discontinue their asthma medications (inhaled corticosteroids and long-acting β agonists) during the run-in period and for remainder of the study.
10. Asthma patients who are stable on low dose ICS or low dose ICS+LABA or who would be stable with low dose ICS as per Investigator's clinical judgement.
11. Currently non-smoking; had not used tobacco products (i.e., cigarettes, cigars, pipe tobacco) within the past year, and having had ≤ 10 pack-years of historical use.
12. Willingness to give their written informed consent to participate in the study.

13. Subjects willing to perform all study related procedures including the use of study inhalers, Spirometry and willing to complete the Subject diary.
14. Female of child-bearing potential, agreed to use a reliable method of contraception during study (e.g., condom + spermicide, IUD, oral, transdermal, injected or implanted hormonal contraceptives).

5.3. Exclusion criteria

1. Life-threatening asthma, a history of asthma episodes(s) requiring intubation, and/or associated with hypercapnia, respiratory arrest or hypoxic seizures, asthma related syncopal episode(s).
2. Hospitalizations within the past year prior to the screening for the conditions mentioned in exclusion criteria No.01 or during the run-in period.
3. Significant respiratory disease other than asthma (COPD, interstitial lung disease, etc.)
4. Evidence or history of clinically significant disease or abnormality including congestive heart failure, uncontrolled hypertension
5. Evidence or history of clinically significant disease or abnormality including uncontrolled coronary artery disease, myocardial infarction, or cardiac dysrhythmia.
6. Historical or current evidence of significant hematologic, hepatic, neurologic, psychiatric, renal, or other diseases that, in the opinion of the investigator, would put the subject at risk through study participation, or would affect the study analyses if the disease exacerbates during the study.
7. Viral or bacterial, upper or lower respiratory tract infection, or sinus, or middle ear infection within four weeks prior to the screening, during the run-in period, or on the day of treatment.
8. Hypersensitivity to Beclomethasone or any of the ingredients of the formulation and any sympathomimetic drug (e.g., Salbutamol) or any inhaled, intranasal, or systemic corticosteroid therapy.
9. Subjects receiving β 2-blockers, anti-arrhythmics, anti-depressants, and monoamine oxidase inhibitors within 4 weeks prior to the screening.
10. Subjects who required systemic corticosteroids (for any reason) within the past 2 months.
11. Clinically significant abnormalities in ECG at screening as per investigators discretion.
12. Female subjects who are pregnant, nursing or planning a pregnancy during the study.

13. Subjects who have participated in another investigational drug or device research study within 30 days of screening.
14. Subjects who are using any medication or has any disease which in the judgment of the Investigator will interfere with the conduct or interpretation of the study.

5.4. Subject Withdrawal

All subjects are free to withdraw from participation in the study at any time, for any reason, specified or unspecified, and without prejudice to further treatment. The criteria for enrollment are to be followed explicitly. If a subject who does not meet enrollment criteria is inadvertently enrolled, that subject will be withdrawn from the study and the Sponsor or AXIS must be contacted. An exception may be granted in rare circumstances where there is a compelling safety reason to allow the subject to continue. In these rare cases, the PI must obtain documented approval from the Sponsor or designee to allow the subject to continue in the study. Subjects who withdraw themselves or withdrawn by PI for lack of efficacy or Adverse events will be provided free available treatment as per the clinical practice of the PI. PI/ study team need to educate the subjects for completion of study and must make all possible efforts to contact the subject if they do not visit the site as per the schedule within window period.

In addition, study drug will be stopped and subject can be withdrawn from the study in the following circumstances:

- The investigator decides that the subject must be withdrawn
 - Subjects who experience asthma exacerbations that requires treatment with systemic corticosteroids, LABA and high dose ICS's
 - If subject develops a medical condition that requires consistent use of prohibited medication
 - Use of rescue medication more than 600 micrograms per day
 - If FEV1 value is < 45 % on Day 21+ 1
 - The subject is unwilling to continue in the study
 - Violation of criteria listed in the Protocol
 - Noncompliance with Protocol
 - Any treated subject who has an adverse reaction to study medication that threatens his/her well-being if continued in the study
 - If the Investigator decides to stop the treatment
 - The Investigator or the Sponsor, for any reason, decides to stop the study
- Subjects who withdraw from the study early will have early withdrawal procedures performed. Subjects who withdraw from the study will not be replaced.

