4.4. Randomization (Day 15 + 1)

Subjects who have completed Run in period will be advised to visit the Investigator site on day 15 + 1 for randomization. Subjects' compliance to the run in period will be assessed with respect to the placebo and rescue medication administration as per the details entered in subject diary.

Subjects who successfully completed the run-in period will undergo exhaled nitric oxide (FeNO) test. Airway reversibility will be checked by performing a bronchodilator test wherein the initial baseline lung volume is measured by spirometer followed by administration of 360 mcg of Salbutamol inhalation and then a repeat lung volume measurement by spirometer within 30 minutes of Inhalation of Salbutamol. Subject's baseline FEV1 readings will be noted before the morning dose. "Baseline morning FEV1 readings at visit 3 will be the average of pre dose highest FEV1 values at two time points (i.e., Patient needs to perform one baseline Spirometry session with minimum of 3 acceptable readings and then after a gap of minimum 30 minutes, one more baseline session will be performed with minimum of 3 acceptable readings. Highest value from both the sessions will be noted. Average of both the highest readings will be considered as baseline FEV1 value).

The subjects who met all the applicable eligible criteria will be randomized to either Test/ Reference/ Placebo groups in a 2:2:1 as per the pre-specified randomization schedule. Subjects will receive their assigned study medication, along with instructions regarding method of administrations. All subjects will be required to take one inhalation twice daily for 4 weeks. The Asthma Control Test (ACT) questionnaire will be evaluated in this visit. The baseline score for the Investigator's Global Evaluation will be recorded.

Study medication, rescue medication (Salbutamol) and subject diary will be dispensed to the subject with a detail instruction regarding how study medication and rescue medication need to be taken and filling instructions of the subject diary.

The first dose of study medication will be administered at the site in the morning to the subject and the subject will self-administer the second dose in the evening at his/ her home.

Table V Procedures from Day 15 +1

Procedure	Treatment Period
	Day 15 +1
Placebo administration compliance (Run in period)	X
Collection of Placebo Canister given in run-in period	X
Eligibility criteria (applicable)	X
General & Systemic Examination	X

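### Sections 5.4 and 4.7 stop drug and force withdrawal for any noncompliance, so a minor deviator found at Visit 4 is lost to PP before the blinded review in 10.2.3

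*Protocol*

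**What the plan says.** Protocol 5.4 introduces its list of triggers by saying that "study drug will be stopped and subject can be withdrawn from the study in the following circumstances". One item is "Noncompliance with Protocol", without a grade, threshold or qualifier. The neighbouring item on violating protocol criteria is equally ungraded. The same section says that withdrawn subjects are not replaced.

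Section 4.7 is stricter: "A subject must be prematurely withdrawn from the study if the subject fulfills any of the withdrawal criteria specified in" Section 5.4. So 5.4 permits withdrawal where 4.7 requires it.

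The scheduled compliance check between randomization and the end of study is at Visit 4, Day 21 ± 1 (Section 4.5): "Compliance of subject diary, study medication and concomitant medication will be checked".

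Section 10.2.3 defines the PP population differently. Deviations are classed as major or minor from blinded data before database lock, and only major ones exclude a subject. Use of 75% to 125% of doses counts as compliant, and Section 9.6 sets the denominator at 56 doses. Subjects who stop early for any reason other than lack of efficacy are excluded from PP but stay in mITT. Under 10.2.2 and 10.4.5, missing end-of-study FEV1 in mITT is filled by last observation carried forward.

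**The concern.** Two parts of the protocol give different answers for the same subject. Under 10.2.3, someone with diary gaps or a few missed doses is a minor deviator who stays in PP. Under 5.4 read with 4.7, the site stops that subject's drug and withdraws the subject weeks before the blinded review takes place. The early stop then excludes the subject from PP automatically.

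PP is the equivalence population, and equivalence alone limits study success: Section 10.1 gives power 0.80 for equivalence against more than 0.99 for superiority. Subjects whom 10.2.3 would keep use up the planned attrition with no safety reason. In mITT, a value from the first week of treatment stands in for a week-4 value that could have been measured. An SAP cannot repair this, because it can neither restart stopped drug nor supply a measurement never taken.

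**Working it through.** **1. Doses due by Visit 4.** Inputs: first dose Day 15 or 16 (Section 4.4), Visit 4 on Day 20 to 22 (4.5), two doses a day, 56 expected (9.6). Doses due before the Visit 4 morning dose = 2 × (Visit 4 day − first-dose day).
- Fewest: 2 × (20 − 16) = 8, or 14% of 56.
- Nominal: 2 × (21 − 15) = 12, or 21%.
- Most: 2 × (22 − 15) = 14, or 25%.

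The PP threshold is 0.75 × 56 = 42 doses. A drug stop at Visit 4 therefore removes the subject from PP even if 4.7 is ignored and the subject is not formally withdrawn. The FEV1 carried forward in mITT was taken 4 to 7 days after the first dose.

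**2. Can the 75% limit be judged at Visit 4?** Doses that may be missed before Visit 4, if all later ones are taken = 2 × (Visit 5 day − first-dose day) − 42.
- Tightest window: 2 × (40 − 16) − 42 = 6.
- Nominal: 2 × (42 − 15) − 42 = 12.

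So Visit 4 is too early to judge compliance against 75%. The converse also matters. Section 4.4 has a supervised start: "The first dose of study medication will be administered at the site in the morning to the subject". On the nominal schedule, a subject who took only that dose before Visit 4 could still reach 1 + 2 × (42 − 21) = 43 of 56 (76.8%). Whether 75% is still reachable is thus far too generous a site-level definition of minor.

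**3. The plan's power figure.** Inputs from Section 10.1: means 0.24 L in both active arms, SD = 1.155 × 0.24 = 0.2772 L, 470 PP subjects per active arm, 90% Fieller interval within 0.80 to 1.25.
- Lower limit: (0.20 × 0.24) / [0.2772 × √((1 + 0.64)/470)] = 2.931 standard errors.
- Upper limit: (0.25 × 0.24) / [0.2772 × √((1 + 1.5625)/470)] = 2.931.
- Power ≈ 2Φ(2.931 − 1.647) − 1 ≈ 0.80.

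The stated 0.80 reproduces. Simulation (2,000,000 trials per sample size) gives 0.801.

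**4. Sensitivity to total mITT-to-PP loss.** The plan allows 588 − 470 = 118 per active arm (20.1%). The loss rates below are assumptions, since the protocol gives no rate of noncompliance found at Visit 4.

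| Total loss | PP per active arm | Equivalence power |
|---|---|---|
| 18% | 482 | 0.814 |
| 20% (plan) | 470 | 0.801 |
| 21% | 465 | 0.796 |
| 22% | 459 | 0.789 |
| 23% | 453 | 0.782 |
| 24% | 447 | 0.774 |

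Each further percentage point (about 6 subjects per active arm) costs roughly 0.6 to 0.8 points of power: (0.801 − 0.789)/2 = 0.006 from 20% to 22%, and (0.789 − 0.774)/2 = 0.0075 from 22% to 24%. The table shows PP attrition in general and does not isolate the part due to this bullet.

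**The case against.** The best defence is that nobody meant the bullet to catch trivial deviations. Other items in the list carry thresholds, such as "If subject develops a medical condition that requires consistent use of prohibited medication" and rescue use above 600 micrograms a day, and these would do little work if any deviation stopped drug. Section 5.4 also says "PI/ study team need to educate the subjects for completion of study". Section 13.3.2 requires deviations to be documented and notified to the ethics committee, not followed by withdrawal. Section 10.2.3 plainly expects minor deviators to reach Visit 5. On this view the bullet is a discretionary power, loosely worded.

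Much of that stands as evidence of intent. It does not remove the compulsory drug stop in 5.4 or the compulsory withdrawal in 4.7. Lenient sites and literal sites, among about 40 centres, would treat the same subject differently.

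The defence is also right that no rate is given and that the planned attrition may cover these subjects. Subjects with major noncompliance would leave PP under 10.2.3 anyway, so only the minor subset counts.

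A reader might infer that the trial is underpowered, or that the test-reference comparison is biased. The documents support neither: power reproduces at the planned loss, and nothing suggests that the rule acts differently on the two active arms. A reader might also blame the lack of spirometry among the "withdrawal procedures including General and Systemic Examination, Vital Signs, Urine Pregnancy Test and Clinical Laboratory Tests" of Section 4.7. That list is not clearly exhaustive, predose FEV1 is already taken at Visit 4, and spirometry at withdrawal would not give a week-4 value.

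**Conclusion.** The inconsistency is real and worth a minor correction. The wording of 5.4 and 4.7 conflicts with 10.2.3 and, if followed literally, removes from PP subjects whom 10.2.3 would keep, while replacing an obtainable week-4 FEV1 in mITT with a first-week value.

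The size is uncertain and probably small. The harm considered here arises from detection at Visit 4; noncompliance first found at Visit 5 costs nothing in this way. Equivalence power drops below 0.80 only if total mITT-to-PP loss exceeds the planned 20%, and then modestly. The effect on superiority is small, given planned power above 0.99. These figures rest on the plan's own means and coefficient of variation and on assumed loss rates.

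**What to change.** - In 4.7, replace must with may for the discretionary 5.4 criteria, so that the two sections agree.
- In 5.4, limit the noncompliance bullet to noncompliance that raises a safety concern, involves prohibited asthma medication, or is persistent or serious in the investigator's judgement. Apply the same limit to the adjacent bullet on violating protocol criteria, as far as it concerns deviations after randomization; otherwise a site could stop the same subject under that bullet.
- In all other cases, re-instruct the subject, continue study drug, take the scheduled Visit 5 FEV1 and document the deviation under 13.3.2. Leave PP membership to the blinded review in 10.2.3.
- Do not define minor at site level by whether 75% of doses can still be reached.
- Leave all safety and worsening triggers, and the rule for subjects enrolled in error, unchanged.

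The cost is amendment wording. Drug is dispensed at Visit 3 and Visit 5 spirometry is already scheduled, so no procedure is added. The downside is that a few imperfectly compliant subjects are dosed and followed for about three more weeks.

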6.0 STUDY ENDPOINTS

6.1. Efficacy Endpoints

Primary Endpoint:

- Mean change in Forced Expiratory volume in 1 second (FEV₁) from baseline (visit 3) to end of study visit (visit 5).

Note: “Baseline morning FEV₁ readings at visit 3 will be the average of pre dose highest FEV₁ values at two time points (i.e., Patient needs to perform one baseline Spirometry session with minimum of 3 acceptable readings and then after a gap of minimum 30 minutes, one more baseline session will be performed with minimum of 3 acceptable readings. Highest value from both the sessions will be noted. Average of both the highest readings will be considered as baseline FEV₁ value). Sampling need to be taken on the same time (with a window period of \pm 30 min) of day as used for first day of a 4 week treatment on the last day of a 4-week treatment.

Secondary Endpoints:

- Mean change in FeNO value from base line (visit 1 & 3) to end of study visit (visit 5)
- Percentage of subjects with reduction of FeNO from Baseline (Visit 1 & 3) to End of Study (Visit 5)

6.2. Safety Endpoints

Safety will be assessed based on reported adverse events, serious adverse events and laboratory assessments.

7.0 ASSESSMENT OF STUDY ENDPOINTS

7.1. Assessment of Efficacy Endpoints

The primary efficacy endpoint will be evaluated on mean change in Forced Expiratory Volume in 1 second (FEV1) from baseline (Visit 3) to end of study (Visit 5).

The secondary efficacy endpoints will be evaluated on mean change in FeNO value from baseline (visit 1 & 3) to end of study visit (visit 5) and percentage of subjects with reduction of FeNO from baseline (visit 1 & 3) to end of study visit (visit 5).

7.2. Assessment of Safety Endpoints

Safety will be assessed based on following for

- Clinical Laboratory investigation
- Vital signs evaluation
- General and systemic examination
- Reported Adverse Events and Serious adverse events

7.2.1. Clinical Laboratory Evaluations

All laboratory investigations shall be performed at designated laboratory (NABL Accredited).

Approximately 15 mL of venous blood for routine tests will be withdrawn at screening and end of study. Additional blood may be withdrawn if deemed necessary.

1. Hematology Panel: Hemoglobin (Hb%), Hematocrit, White blood cell count (WBC), Total differential count, Red blood cell count (RBC), Platelet count
2. Renal function tests: BUN, Creatinine
3. Liver function tests: Albumin, Alkaline phosphatase, Total bilirubin, Aspartate aminotransferase (AST) and Alanine aminotransferase (ALT)
4. Random blood sugar
5. Serum electrolytes: Sodium, Potassium and Chloride
6. Serum pregnancy test (at screening only for females of child bearing potential)

Additional laboratory evaluations may be performed, if deemed necessary (for safety reasons), but should be informed to the Medical Manager / CRA and shall be notified to the EC. Any unscheduled lab test required by the Investigator for safety reasons, site specific local laboratory can be approached.

